**6.2 Visit 2**

Subjects will undergo repeat assessment at six months following randomization. This will include anthropometry (similar to baseline), a fasting blood draw and endoscopy with research biopsies and brushings as outlined at baseline. Subjects will also fill out the Reflux Symptom Questionnaire (RSQ)/GER Questionnaire. Remaining medication will be counted and recorded.

If the participant is to be scheduled for a clinically indicated upper endoscopy and procedures that are ordered cannot be done on the Clinical Research Unit, (i.e. radiofrequency ablation, endoscopic mucosal resection, esophageal dilation, endoscopic ultrasound) the research portion of the procedure will be done during the clinically indicated upper endoscopy. These research procedures will include biopsies and brushings of the esophagus as well as mucosal impedance.

**Schedule of Events**

Study Activity	Month 0	Month 1	Month 2	Month 3	Month 4	Month 5	Month 6	Month 6 + 7 days
Informed consent	X							
History	X							
Concurrent meds	X							
Physical exam (ht, wt, hip/waist, VS)	X						X	
Blood draw (FFA, LDL, AST, ALT) INR )	X						X	
Endoscopy with bx/brushing and mucosal impedance measurement	X						X	
Randomization	X							
Adverse event evaluation		X	X	X	X	X	X	X
Pill count		X	X	X	X	X	X	
Single slice CT scan of abdomen	X							
Questionnaire	X						X	

## 7 Statistical Plan

### 7.1 Sample Size Determination

#### Statistical Analysis

Up to 90 patients with Barrett's will be identified and randomized to either drug or placebo. The primary analysis objective in this pilot study is to estimate response magnitude and variation which will be the information needed to design a larger adequately powered study to study the efficacy of  $\omega$ 3FFA as a chemoprevention agent in BE. The data will be summarized as mean, standard deviation, as well as median, and interquartile range, overall (baseline) and by treatment group (post-supplementation at 6 months). In addition, 95% confidence intervals for response mean (or median) treatment group values and 95% confidence intervals for treatment group differences in means (or medians) will also be calculated. Exploratory descriptive summaries of the response data will also be generated after stratifying on ASA intake.

Aim 1: The primary response outcome is tissue PGE2 levels and the main secondary response outcome is the histologic score of 3 or 4 (severe grades of inflammation). Other secondary outcomes include pre and post supplementation serum and tissue  $\omega$ 3 FFA levels.

Aim 2: The primary response outcome is the Cytokine expression profile in esophageal biopsies as measured by qPCR [IL1 $\beta$ , IL6 (M1 markers) versus IL1, IL10 (M2 markers)]. Secondary response outcomes include change in esophageal macrophage counts and phenotype proportions (total, %M1, %M2).

Aim 3: The esophageal mucosal impedance of the squamous epithelium and columnar epithelium will be summarized as mean (SD) or median (IQR) depending on data normality. The data will be summarized (baseline and post-supplementation) by treatment group. Change in impedance (Baseline – post supplementation) will be compared using appropriate statistical tests. Secondary outcome analysis will include testing the association between esophageal mucosal impedance and measures of central obesity (including waist circumference, waist hip ratio and abdominal visceral fat area on CT scan).

Aim 4:

We will align the paired end reads using PANDASeq given our small amplicon size (~392bp) which allows for significant overlap in the two reads. Data will be processed using QIIME1.8.0 (Quantitative Insights Into Microbial Ecology) analysis pipeline. OTUs (Operational Taxonomic Units) will be determined at 97% sequence similarity using uclust, taxonomy will be assigned using RDP classifier against the GreenGenes database, and a phylogenetic tree will be built using FastTree. The OTU table will be rarified at a single sequencing depth. We will compare alpha diversity using both phylogenetic (PD whole tree) and non-phylogenetic measures (Shannon, observed species and Chao1) to assess evenness and richness of distribution. We will compare beta diversity using both phylogenetic (UniFrac) and count based metrics (Bray-Curtis).

Statistical analysis of differences between groups and changes within the microbiome will be performed such as using PERMANOVA to compare beta diversity. Differences in individual taxa between groups will be assessed using ANOVA with correction for multiple hypotheses testing using FDR. A p-value of <0.05 will be considered statistically significant. Additional

analysis to impute potential changes in gene content (PICRUSt) and pathways (HUMANN) will be done depending on the results of initial analysis.

**Pitfalls and Alternative approaches:** It is possible that recruitment to this trial may be challenging. However, more than 400 patients with BE are seen annually in Rochester and the PI has successfully led and participated in many prospective studies which have recruited BE patients for clinical trials. It also possible, though unlikely, that the in-vitro effects of  $\omega$ 3 FFAs may not translate into clinical effects in terms of alterations in tissue PGE2 and macrophage counts. We will also consider assessing the influence of  $\omega$ 3 FFA on BE cell survival, a known biological correlate to neoplastic progression in BE, using Ki-67-Caspase dual staining to assess other biologic effects of  $\omega$ 3 FFA. Concomitant ASA use may confound the effects on PGE2 levels. Given that this is a preliminary study, we will collect data on ASA and NSAID use and perform analysis stratified on ASA and NSAID use. The randomized study design will however mitigate this confounding effect to a large extent. It is possible that the dose of  $\omega$ 3 FFA used in this proposal may be inadequate for a clinical effect in vivo. We have chosen the 3.6 grams/day dose as described in prior human clinical trials: this dose has been shown to be well tolerated and able to produce meaningful clinical response in human trials. We also have proposed to target subjects with a BMI>30 given that these subjects with increased visceral fat are most likely to benefit from  $\omega$ 3 FFAs.

**Feasibility and Timeline:** We anticipate recruitment to be complete in 6-9 months following IRB approval (which has been initiated). Assays and analysis should be completed in 3 months following completion of the trial and publication thereafter. Assays have been previously performed and validated in multiple published manuscripts by collaborators and Core laboratories. Preliminary data obtained from this trial will be crucial in supporting an aim of a R01 application focused on assessing the mechanistic relationship between BE and central obesity.

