## 2 Study Objectives

Specific Aim 1: To estimate the magnitude and variation of changes in esophageal inflammation and injury in BE as measured by tissue PGE2 and the esophageal inflammation score, attributable to  $\omega$ 3 FFA supplementation.

Specific Aim 2: To estimate the magnitude and variation of changes in esophageal macrophage infiltration and modulation of esophageal macrophage phenotype attributable to  $\omega$ 3 FFA supplementation.

Specific Aim 3: To estimate the magnitude and variation in changes in esophageal mucosal impedance attributable to  $\omega$ 3 FFA supplementation.

Specific Aim 4: To define the baseline esophageal mucosal microbiome and the potential change in the esophageal mucosal microbiome attributable to  $\omega$ 3 FFA supplementation.

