### 3.2 Study Endpoints

The primary analysis objective in this pilot study is to estimate response magnitude and variation in esophageal inflammation and injury in BE as measured by tissue PGE2, the esophageal inflammation score, esophageal macrophage infiltration and modulation of esophageal macrophage phenotype attributable to  $\omega$ 3 FFA supplementation. This will be the information needed to design a larger adequately powered study to study the efficacy of  $\omega$ 3 FFA as a chemoprevention agent in BE.

**Aim 1:** The **primary response** outcome is tissue PGE2 levels and the main secondary response outcome is the histologic score of 3 or 4 (severe grades of inflammation). Other **secondary outcomes** include pre and post supplementation serum and tissue  $\omega$ 3 FFA levels.

**Aim 2:** The **primary response** outcome is the cytokine expression profile in esophageal biopsies as measured by qPCR [IL1 $\beta$ , IL6 (M1 markers) versus IL1, IL10 (M2 markers)]. **Secondary response outcomes** include change in esophageal macrophage counts and phenotype proportions (total, %M1, %M2).

**Aim 3:** The primary response outcome is change in esophageal mucosal impedance (baseline-post treatment) which is a physiologic correlate of the epithelial barrier function, with  $\omega$ 3 FFA supplementation. Secondary outcomes include the association of esophageal mucosal impedance with measures of central obesity (waist circumference, waist hip ratio and abdominal visceral fat area on CT) at baseline and following treatment.

**Aim 4:** The primary response outcome is the change in the esophageal microbiome in BE subjects following  $\omega$ 3 FFA supplementation. Secondary outcomes will be the association of the microbiome pattern with measures of central obesity ((waist circumference, waist hip ratio and abdominal visceral fat area on CT).

Assays performed at baseline and at 6 months will include:

*Aim 1:* Primary outcome: Tissue PGE2 in esophageal biopsies. This will be performed by previously described methods [21] on esophageal biopsies snap frozen at -80^0 C in [name] laboratory.

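### For tissue PGE2 (Aim 1) and the qPCR profile (Aim 2), section 7.1 does not define response as change and names no baseline adjustment, SD of change or pre-post correlation, although both aims are to estimate changes

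*Combined protocol and SAP*

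**What the plan says.** Section 2 sets Aim 1 as "To estimate the magnitude and variation of changes in esophageal inflammation and injury in BE", measured by tissue PGE2 and the inflammation score, and Aim 2 as "To estimate the magnitude and variation of changes in esophageal macrophage infiltration and modulation of esophageal macrophage phenotype". Sections 3.2 and 7.1 give the primary analysis objective as estimating response magnitude and variation, to inform the design of a larger study.

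For the data in general, section 7.1 lists:

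- mean, SD, median and interquartile range, "overall (baseline) and by treatment group (post-supplementation at 6 months";
- 95% confidence intervals for arm means or medians;
- between the arms, "95% confidence intervals for treatment group differences in means (or medians) will also be calculated";
- exploratory descriptive summaries stratified by aspirin use.

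On Aim 1, section 7.1 states: "The primary response outcome is tissue PGE2 levels". The Aim 2 primary outcome is a cytokine expression profile by qPCR. Neither is worded as a change.

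Other outcomes are. In section 7.1, Aim 2: "Secondary response outcomes include change in esophageal macrophage counts and phenotype proportions". In section 3.2, Aim 3: "The primary response outcome is change in esophageal mucosal impedance (baseline-post treatment", and Aim 4: "The primary response outcome is the change in the esophageal microbiome in BE subjects". For impedance, section 7.1 also plans summaries by arm at both time points and a comparison of change.

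Section 3.2 places the Aim 1 and Aim 2 assays at baseline and at 6 months, and the Schedule of Events has endoscopy with biopsy at both visits. Paired values of PGE2 and the qPCR markers will therefore exist.

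**The concern.** The objective is worded as change, but the outputs listed for the two primary tissue outcomes are a baseline table pooled over arms and a 6-month table by arm. Three things follow if the plan is carried out as it most naturally reads.

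- **Precision.** Each participant's own baseline value is measured but not used in the arm comparison.
- **Chance imbalance.** With baseline shown only overall, a difference between the arms at baseline would neither appear in the tables nor be adjusted for.
- **Planning information.** The variation of change, which the aims name, cannot be recovered from the listed summaries.

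It is also unclear which quantity the intervals describe. A 6-month contrast and a contrast of change scores have the same expectation under randomisation, but their widths can differ a good deal.

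**Working it through.** **Inputs.** From section 3.1: 80 completers, 40 per arm. From section 7.1: up to 90 randomised (45 per arm if split equally) and 95% intervals. The documents state no effect size, SD, correlation or target precision for these outcomes, so there is no figure of the plan's own to reproduce. Assumed: pre-post correlation r of 0.3, 0.5 or 0.7, with 0.1 as a low case. The unit is the 6-month SD, taken as common to both arms.

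**Step 1: can the listed summaries give the variation of change?** With s0 the baseline SD and s1 the 6-month SD,

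SD of change = sqrt(s0² + s1² − 2·r·s0·s1).

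The planned tables supply s0 (pooled) and s1 (by arm), but not r. With s0 = s1 = 1 this is sqrt(2(1 − r)) = 1.18, 1.00 or 0.77 at r = 0.3, 0.5 or 0.7. The same tables are compatible with all three values. Stratifying by aspirin use does not supply r.

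**Step 2: half-width of the 95% CI for the arm difference, 40 per arm.**

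- 6-month values, unadjusted: t(0.975, 78)·sqrt(2/40) = 1.991 × 0.2236 = 0.445, whatever r is.
- ANCOVA on the outcome's own baseline: t(0.975, 77)·sqrt((2/40)·(1 − r²)·(1 + 1/76)). The 77 reflects the lost degree of freedom, and 1/76 is the average cost of chance covariate imbalance. At r = 0.5: 1.991·sqrt(0.05 × 0.75 × 1.0132) = 0.388.
- Change scores, equal SDs: 0.445·sqrt(2(1 − r)).

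| r | 6-month, unadjusted | ANCOVA | Reduction with ANCOVA | Change score (equal SDs) |
|---|---|---|---|---|
| 0.1 | 0.445 | 0.446 | none | 0.597 |
| 0.3 | 0.445 | 0.428 | 4% | 0.527 |
| 0.5 | 0.445 | 0.388 | 13% | 0.445 |
| 0.7 | 0.445 | 0.320 | 28% | 0.345 |

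ANCOVA breaks even at r of about 0.12. With 45 per arm the unadjusted half-width is 0.419, against 0.402, 0.365 and 0.301 with ANCOVA at r = 0.3, 0.5 and 0.7.

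**Step 3: how much the meaning of response matters.** With k = s0/s1, the change-score half-width is 0.445·sqrt(1 + k² − 2rk), which exceeds the 6-month half-width when r < k/2. At r = 0.3 it is 0.460 for k = 0.7, 0.527 for k = 1 and 0.658 for k = 1/0.7. The ANCOVA width does not depend on k.

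**Step 4: chance imbalance.** A baseline difference of one standard error is sqrt(2/40) = 0.224 baseline SD. On average it moves the unadjusted 6-month difference by r × 0.224 = 0.07, 0.11 or 0.16 SD at r = 0.3, 0.5 or 0.7.

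**Step 5: scale.** Item 5 of the preliminary data in section 1.1 gives mean PGE2 of 42 and 2 pg/mg in two groups of 10, p = 0.03. If that p came from a t-test and the spread in the uninjured group was negligible (both assumed), the SD in the injured group is about sqrt(10) × 40/t. This is 54 with t = 2.356 (18 df) and 49 with t = 2.574 (9 df). Either exceeds the mean of 42, which suggests marked right skew and favours choosing a log scale in advance. Item 9 of the same section analysed qPCR as delta-Ct, which is already logarithmic.

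**The case against.** The best defence is that the text is ambiguous rather than wrong. The sentence on confidence intervals says neither unadjusted nor 6-month. The aims speak of changes attributable to supplementation, so response could be read as change. The word level proves little, since the same Aim 1 paragraph lists pre- and post-supplementation fatty-acid levels. This stands in part: a reader might infer that section 7.1 commits to an unadjusted 6-month comparison, but that is only the plain reading of a plan that names no model, covariate or change score. The ambiguity does not remove the need for wording. Section 7.1 says change for the Aim 2 secondary outcomes and for impedance, and leaves it out for these two.

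It can also be said that the trial is an estimation pilot, that the gain depends on an unknown r, that at r = 0.3 it is only 4%, and that the SD of change could be computed later. The first three are true and limit the size of the point. The last shows that the fix is cheap, not that the plan contains it. Estimation is the pilot's stated purpose, so these quantities belong among its planned outputs.

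Two stronger readings should be resisted. One is that the planned comparison is biased: it is not, because allocation is randomised. The other is that the larger trial would be sized wrongly by a known percentage. The documents name neither its endpoint nor its analysis, and the Significance and Innovation text in section 1.1 describes its goal as lower adenocarcinoma incidence. A sample-size penalty calculated on these markers would therefore be speculation.

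**Conclusion.** The point holds and should be fixed. For the primary outcomes of Aims 1 and 2, section 7.1 does not specify the change that the aims set out to estimate, and it makes no stated use of the paired baseline. On the plain reading, the cost is a 95% CI half-width of 0.445 SD where ANCOVA would give 0.428, 0.388 or 0.320, together with tables that lack by-arm baseline values, the SD of change and the pre-post correlation.

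The widths assume 40 completers per arm, a common 6-month SD, a roughly linear relation to baseline, and r between 0.3 and 0.7. If r is near 0.1 the precision argument falls away. The reporting gap remains at any r. No bias and no safety issue is claimed.

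**What to change.** In section 7.1:

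1. Define response for PGE2 and for each qPCR marker.
2. Estimate the 6-month arm difference with its 95% CI by ANCOVA on the same outcome's baseline value from the same biopsy site. Name the site: section 4.3 samples the gastroesophageal junction, the Barrett's mucosa and the squamous mucosa.
3. Fix the scale in advance: log PGE2, reported as a geometric mean ratio, and delta-Ct for qPCR with no further log.
4. Apply this marker by marker once the primary list is settled. The outcome statements in sections 3.2 and 7.1 give IL1β and IL6 against IL1 and IL10. The assay list in section 3.2 gives CD68, TNFα, MCP1, CD206, IL1 and IL10.
5. Report baseline and change by arm, the SD of change, the ANCOVA residual SD and the pre-post correlation with its CI. Keep the planned means, medians and interquartile ranges as descriptive output.

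The cost is some wording, one degree of freedom per model and a little more analysis. Both assays are already planned at both visits, so no new data, procedures or participants are needed.

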**Preliminary data:**

1. *Increased visceral and GE junction fat area are independently associated with BE, esophageal inflammation and HGD [5].* GE junction, visceral and subcutaneous (SQ) fat area were assessed in age and gender matched 50 BE cases and 50 controls, using CT scans. BE was strongly associated with visceral and GE junction fat area independent of BMI. There was no association with SQ fat area, suggesting a non-mechanical influence of visceral fat on BE pathogenesis. Furthermore, increased visceral fat area (but not SQ fat area) was also independently associated with severe esophageal inflammation and HGD, further suggesting a non-mechanical influence of visceral fat on esophageal inflammation and carcinogenesis.

2. *Metabolic Syndrome is a risk factor for BE independent of reflux[6].* We studied the association between BE and metabolic syndrome in a population based case control study: 309 subjects from Olmsted County, MN were studied (103 BE cases, 103 reflux + controls and 103 reflux - controls). 64% of cases, 49% of reflux + controls and 51% of reflux - controls had MetS. MetS was associated with a 2 fold increased risk of BE with reflux (+) controls (OR 1.9, 95% CI 1.1, 3.6, p=0.04) and reflux (-) controls (OR 1.9, 95% CI 1.1, 3.4 p=0.04) on multivariable regression analysis.

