Secondary outcomes: 1. Tissue inflammation score (grade 0-3). This will be performed on esophageal H&E stained sections as previously described [5], by [name], an experienced gastrointestinal pathologist. 2. Esophageal tissue EPA levels: this will be performed on esophageal biopsies obtained at baseline and at 6 months, in the Metabolomics Core laboratory. 3. Serum  $\omega$ 3 FFA levels: will be performed using mass spectroscopy/liquid chromatography in the Immunochemistry Core laboratory at baseline and 6 months.

*Aim 2:* Primary outcome: 1. Quantification of esophageal macrophage infiltration (and subtypes) by qPCR for CD68 (macrophage marker) TNF $\alpha$  and MCP1 (M1 markers) and CD206, IL1, IL10, as M2 markers). This will be performed in collaboration with [name] (see preliminary data and letter of support) using previously described standard methodology [29].

Secondary outcomes : Esophageal macrophage counts (using CD68 and HAM 56 as markers) and proportion of M1 and M2 (CD206) using immunofluorescence will be performed using previously described methods [24]. Cells double labeled for CD206 and CD68 will be categorized as M2 cells and those staining only with CD68 will be categorized as M1 cells. Cell counts will be performed as previously described.

Aim 3: Esophageal mucosal impedance measurements will be obtained using a esophageal mucosal impedance catheter at 2 cm, 5 cm and 7 cm above the GEJ. At least one measurement will be obtained in the squamous mucosa at 3 cm above the BE segment [30].

Aim 4: The esophageal microbiome will be characterized from biopsies and brushings from the squamous and columnar epithelium using standard methods.

Sequencing : Biopsy samples and brushings will be collected in cryo-vials and flash frozen in liquid nitrogen. All samples will be stored at -80 till they are ready for processing.

Next Generation sequencing:

Bacterial DNA will be enriched in biopsy and brushings using NEBNext microbiome DNA enrichment kit if concentrations are low. Amplicons spanning the variable region 4 (V4) of bacterial 16SrRNA will be generated using a barcoded reverse primer (515F, 806R). Samples will be sequenced using the MiSeq platform at Mayo Genome Facility to obtain 300bp paired end reads. Based on our previous experience we will sequence at most 100 samples in one sequencing run and we expect ~30,000 high quality reads per sample.

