#### 4.2 **Exclusion Criteria**

- Allergy to  $\omega$ 3 FFAs, fish or shellfish.
- Presence of high grade dysplasia or cancer on histology.
- Pregnant and or breastfeeding women
- Presence of esophagitis on initial endoscopy or symptoms of refractory GERD (heartburn or regurgitation  $\geq 2$  times a week) indicative of uncontrolled gastroesophageal reflux.
- Inability to give informed consent.
- Currently taking  $\omega$ 3 FFA as prescription.
- Anti-coagulant therapy (Plavix, Warfarin, Coumadin)
- AST or ALT level  $>$  three times upper limit of normal at baseline
- LDL  $> 200$  mg/dl at baseline.
- INR  $> 2$

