#### 4.3 **Subject Recruitment, Enrollment and Screening**

Subjects between 18-85 years of age, with known BE (no dysplasia and low-grade dysplasia) will be identified using an existing GI database for participation in this study. Invitation letters will be mailed to eligible subjects. Subjects will be called to discuss study and scheduled for a screening visit. Subjects taking  $\omega$ 3 FFA as a supplement will discontinue use at least four weeks prior to visit 1. Subjects will report fasting 12 hours for this visit. Subjects meeting inclusion and exclusion criteria will be screened and consented. Baseline assessment will include the measurement of height, weight, waist circumference, hip circumference and waist/hip ratio using standard methods of anthropometric measurements. A comprehensive medication list will be obtained. Patients will also fill out the Reflux Symptom Questionnaire (RSQ)/GER Questionnaire a validated instrument to assess reflux symptoms All patients will continue their baseline PPI regimen to control gastroesophageal reflux. 20cc of blood will be drawn after 12 hours of fasting to obtain a baseline serum FFA profile . Clinical baseline blood will be drawn for inclusion/exclusion: INR, LDL, AST and ALT. Endoscopy will then be performed in a standard manner. Six biopsies will be obtained from the GE junction, and seven biopsies from the BE mucosa 1 cm above the GE junction. Two biopsies from each site will be formalin fixed and paraffin embedded (for inflammatory score assessment) and the remainder frozen at  $-80$  C for subsequent analysis. An additional seven biopsies will be obtained from the squamous mucosa at least 3 cm above the proximal end of the BE segment. Two will be placed in formalin (or other fixative) and paraffin embedded (IHC for macrophage cell counts) and the remainder will be snap frozen at  $-80^{\circ}$  C (PGE2 levels). Endoscopic brushings of the Barrett's segment as well as squamous tissue will be obtained and frozen for each subject. Endoscopic mucosal impedance measurement will be completed during endoscopy. A single slice CT scan of the

abdomen will also be obtained at baseline for each subject to quantify visceral and subcutaneous fat area in the abdomen.

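### Aim 1 gives priority to a severe/not-severe cut over the full histologic inflammation score, which loses precision at every severe rate tried

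*Combined protocol and SAP*

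**What the plan says.** Section 2 sets Aim 1 as estimating the size and variability of change in "esophageal inflammation and injury in BE as measured by tissue PGE2 and the esophageal inflammation score". The outcome text in Section 3.2 and the analysis text in Section 7.1 then state that "the main secondary response outcome is the histologic score of 3 or 4 (severe grades of inflammation"). The assay list in Section 3.2, covering baseline and 6 months, has among its Aim 1 secondary outcomes "Tissue inflammation score (grade 0-3"), with no cut and no grade 4.

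Section 7.1 plans means, SDs, medians and interquartile ranges, with 95% intervals for arm means or medians and their differences. It names no ordinal method, baseline adjustment or shift table for the score.

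On the cohort, Section 4.2 excludes "Presence of esophagitis on initial endoscopy or symptoms of refractory GERD", and Section 4.3 states: "All patients will continue their baseline PPI regimen to control gastroesophageal reflux". No expected frequency of severe grades is given anywhere.

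**The concern.** A cut at the severe end records only movement across that one boundary. A subject who goes from grade 2 to 1, or from 1 to 0, counts as unchanged. The cut therefore cannot describe how large the change in the score is or how it varies, which is what Aim 1 asks for and what the later, larger trial would be designed from.

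The full score is collected, so nothing is lost at the data level. What is at stake is which version has priority and whether the other has a stated analysis. As written, the less precise version comes first and the more precise one has no method of its own.

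**Working it through.** There is no figure in the plan to reproduce: Section 7.1 gives no severe rate, effect size, SD or power. The check compares the precision of the two versions over a range of assumed severe rates. It does not use baseline values.

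**Inputs**
- n = 40 per arm, N = 80 (Section 3.1).
- Four grades, 0 to 3 (Section 3.2 assay list), with severe taken as the top grade.
- Common odds ratio of 2.5 in favour of active (assumed; 0.4 for being in a worse grade).
- Control percentages in grades 0/1/2/3 (assumed): 35/40/20/5, 30/35/25/10, 25/30/25/20, 20/25/25/30 and 15/20/15/50.

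**Step 1, active arm.** Multiply the odds of being at or below each grade by 2.5. In the 10% case the control cumulative proportions 0.30, 0.65 and 0.90 have odds 0.429, 1.857 and 9. These become 1.071, 4.643 and 22.5, that is, 0.517, 0.823 and 0.957. The active severe rate is 4.3%.

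**Step 2, interval from the cut.** Variance of the log odds ratio = 1/[n p1(1 − p1)] + 1/[n p2(1 − p2)]. In the 10% case: 1/(40 × 0.10 × 0.90) + 1/(40 × 0.0426 × 0.9574) = 0.278 + 0.613 = 0.891, so SE = 0.944. Upper/lower limit ratio = exp(2 × 1.96 × 0.944) = about 41.

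**Step 3, interval from the full score.** Proportional-odds information = (N/12)(1 − Σ m³), where m is the mean of the two arms' proportions in each grade. In the 10% case m = 0.409, 0.328, 0.192 and 0.071, and Σ m³ = 0.111. Information = 6.667 × 0.889 = 5.93, SE = 0.411, ratio = exp(2 × 1.96 × 0.411) = about 5.0.

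**Step 4, share of information kept.** On the same averaged basis the cut's information is (N/4) m(1 − m) for the severe grade: 20 × 0.0713 × 0.9287 = 1.32. Then 1.32/5.93 = 22%.

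| Control severe rate | Expected severe cases, control vs active | Information kept by the cut | Limit ratio, cut | Limit ratio, full score |
|---|---|---|---|---|
| 5% | 2.0 vs 0.8 | 12% | 183 | 5.2 |
| 10% | 4.0 vs 1.7 | 22% | 41 | 5.0 |
| 20% | 8.0 vs 3.6 | 41% | 14 | 4.9 |
| 30% | 12.0 vs 5.9 | 56% | 9 | 4.8 |
| 50% | 20.0 vs 11.4 | 78% | 6 | 4.9 |

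The 5% row is a large-sample figure on about three events, so it mainly shows that the odds ratio could hardly be estimated. There the chance that at least one arm has no severe case is 1 − (1 − 0.95^40)(1 − 0.9794^40) = 1 − 0.871 × 0.565 = about 51%.

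**Sensitivity to the distribution.** If most controls are at grade 0, the full score also loses precision. For 85/7/3/5, Σ m³ = 0.710 and the information is 1.93: the full-score ratio is about 17 against 183, and the cut keeps 20 × 0.0353 × 0.9647/1.93 = 35%. For 70/15/5/10, Σ m³ = 0.471 and the information is 3.53: the ratio is about 8 against 41, and the cut keeps 1.32/3.53 = 38%. The full score is more precise in every case tried.

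**The case against.** The strongest reply is that nothing is thrown away. The uncut score is listed as a secondary outcome, and Section 7.1's general summaries do not exclude it, so a 2-to-1 shift would be recorded and could be reported. That stands. The criticism is confined to priority and to the missing method.

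A reader might infer that few severe cases are to be expected. The documents do not support that as a fact. The exclusion concerns esophagitis seen at endoscopy, whereas the outcome is histologic and read on GE-junction and Barrett's biopsies: "Two biopsies from each site will be formalin fixed and paraffin embedded (for inflammatory score assessment"). The preliminary data in Section 1.1 also report that "increased visceral fat area (but not SQ fat area) was also independently associated with severe esophageal inflammation and HGD", and this cohort is selected for obesity or a large waist. That finding gives no frequency either.

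A reader might also infer that most of the information is always lost. Under the main distributions above, that holds at severe rates up to 20% but not at 30% or 50%.

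Power comparisons look more dramatic: with the same odds ratio, Fisher's test on the cut has about 0.6% power at a 5% severe rate, against 58–61% for a rank test on the full score. But Fisher's test is conservative with sparse events, and an ordinary two-proportion approximation gives about 11%. The plan names neither test, and its stated purpose is estimation, so interval width is the fairer measure.

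Nor are the planned summaries invalid for a binary outcome. The mean of a 0/1 variable is a proportion, and a difference in means is a risk difference. Only the median would be uninformative, and only if fewer than half of each arm is severe.

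Finally, a severe-grade outcome is a legitimate choice with a direct reading. That is a reason to keep it as a summary, but it does not answer Aim 1's question about change in the score.

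**Conclusion.** The point holds as a matter of priority and precision. The main secondary outcome does not match what Aim 1 sets out to estimate, and it is less precise than the full score already being read. Under the main assumed distributions the 95% limit ratio is about 183 down to 6 for the cut, against about 5 for the full score. The cut keeps about 12% to 78% of the information as the control severe rate goes from 5% to 50%.

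These sizes rest on 40 per arm, four grades, proportional odds with a ratio of 2.5, and grade distributions that are assumptions. Proportional odds itself favours the ordinal analysis. The direction did not change in any case tried, so the recommendation does not depend on the unknown severe rate.

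The scale itself is contradictory: a score of 3 or 4 in the outcome and analysis text, grades 0 to 3 in the assay list. On the 0-to-3 scale only grade 3 can count as severe. On a scale with a grade 4, two grades would count and the severe rate would differ. The documents do not show which was meant.

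**What to change.** 1. Reconcile the scale in Sections 3.2 and 7.1, and state which grades are called severe.
2. In both sections, make the full ordinal score the main secondary outcome. Analyse the month-6 score by arm with the baseline score as covariate, using a proportional-odds model, or a rank-based method if that assumption fails. Report the effect with a 95% CI, together with a baseline-to-month-6 shift table by arm.
3. Keep the proportion with a severe grade, by arm and with its CI, as a descriptive summary.

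The cost is wording in two sections. No new data are needed, since the score is already read at both visits. The small downside is reliance on a proportional-odds assumption and a less direct headline than the percentage with severe inflammation; the shift table and the retained proportion largely cover both.
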